#### 17.2.2.10. Liver dysfunction at any time during 28 days post baseline

The total number of patients experiencing any liver dysfunction during the 28 days post baseline will be presented. The effect of RDV on the risk of this complication will be evaluated using the same methodology as used in 17.2.1 above.

## 18. Missing data and Withdrawals

It is anticipated that there will be a degree of missing data, and that some outcomes may not be accurately measurable for all patients. A key impact of missingness will be in the matching process – a propensity score is only calculable for patients with complete data with respect to matching variables. If sample sizes are significantly reduced, it may be necessary to reduce the number of matching variables. If there is a large amount of missing comorbidity data, we will consider changing measures from individual comorbidities, to a measure of ‘number of comorbidities ticked’. All decisions on missing data handling will be documented, but cannot easily be predefined prior to seeing the data.

In the case of missing time-to-event data, censoring will be used so that at least some data may be included.

Accounting for types of missingness – missing at random, missing completely at random, and missing systematically is beyond the scope of the analysis.

Any patient that withdraws permission for their data to be analysed will be excluded from all analyses.

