## 8.8. Sequence and duration of study periods

All patients are followed up until discharge, death, or 28 days post baseline – whichever occurs first.

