## 17.2.2. Secondary Outcomes

### 17.2.2.1. Time to recovery

Recovery is defined as discharge from hospital or continued hospitalisation with no on-going health-care needs related to COVID-19. For patients that recover, a time-to-event is defined as the number of days from baseline to discharge, or from baseline to cessation of COVID-19 related health-care (whichever occurs first). All other patients are censored at last available follow-up or 28 days (whichever occurs first). All deaths before 28 days (with no prior recovery) will be censored at day 28g. A Cox proportional hazards model will be used to model time-to-recovery, fitting treatment as a covariate, and adjusting for the key confounders: age, sex, and number of comorbidities at baseline. The hazard ratio comparing RDV with controls estimated from the model will be presented together with a 95% CI and a p-value. Kaplan-Meier graphs comparing recovery by treatment group will be presented – for the full matched cohort; and for key age-groups: <50, 50-59, 60-69, 70-79, ≥80 years.

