#### 17.2.2.6. Time-to-first ventilation

The DAILY CRF will be used to define, where possible, date of first use of ventilation. Any patient not recorded as ventilated that is lost to follow-up or dies before 28 days, will be censored at the date of last follow-up, or date of death. This outcome will be analysed as a time-to-event using the methodology described in 17.2.2.1 above.

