#### 17.2.2.7. Use of non-invasive ventilation at any time during 28 days post baseline

The total number of patients requiring any non-invasive ventilation during the 28 days post baseline will be presented. The effect of RDV on the risk of requiring non-invasive ventilation will be evaluated using the same methodology as used in 17.2.1 above.

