#### 17.2.2.8. Use of mechanical ventilation / ECMO at any time during 28 days post baseline

The total number of patients requiring any mechanical ventilation/ECMO during the 28 days post baseline will be presented. The effect of RDV on the risk of requiring mechanical ventilation/ECMO will be evaluated using the same methodology as used in 17.2.1 above.

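### Time-to-first ventilation has no rule for a patient known to be ventilated but without a first date, and section 18 read literally would censor that known event

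*SAP*

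**What the plan says.** SAP 17.2.2.6 names one source for the event date and accepts that it may fail: "The DAILY CRF will be used to define, where possible, date of first use of ventilation". Its censoring rule then covers a limited set of patients: "Any patient not recorded as ventilated that is lost to follow-up or dies before 28 days, will be censored" at last follow-up or death. For the model it refers back: "This outcome will be analysed as a time-to-event using the methodology described in 17.2.2.1 above". Section 17.2.2.1 censors patients without the event at last follow-up or day 28, whichever is earlier.

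Section 18 adds a rule for all time-to-event outcomes: "In the case of missing time-to-event data, censoring will be used so that at least some data may be included". It does not separate a missing date from an unknown event status, and it gives no censoring time.

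Outcomes 7 and 8 are yes/no measures over the same 28 days. Section 17.2.2.7 says: "The total number of patients requiring any non-invasive ventilation during the 28 days post baseline will be presented". Section 17.2.2.8 says: "The total number of patients requiring any mechanical ventilation/ECMO during the 28 days post baseline will be presented". Neither needs a date, and neither names the form it is taken from.

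**The concern.** Right-censoring fits a patient whose event status is unknown after some day. A patient who is known to have been ventilated, but whose first day is missing, is a different case: the event happened and only its time is incomplete. Censoring that patient discards the event. If the censoring time is late, it also adds days that are counted as ventilation-free when they may not have been.

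Two things are at stake for outcome 6. The ventilation curve would be too low, with fewer events behind the hazard ratio. If first dates are missing more often in one group, that group would look better protected than it is.

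Unequal loss is plausible. Section 8.9 ties some collection days to RDV dosing and RDV initiation, which could make RDV patients easier to date than controls. That direction is an inference; the SAP does not state it. Section 17.2.2.5 treats unequal missing Daily CRFs as a threat to the oxygen outcome and sets a 10-point tolerance. Time-to-first ventilation uses the same form and has no such check.

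**Working it through.** **Which rule applies**

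| Patient | Rule in the SAP | Outcome 6 |
|---|---|---|
| Ventilated, first day on Daily CRF | 17.2.2.6 | Event |
| Not recorded as ventilated, lost or died | 17.2.2.6 | Censored |
| Recorded as ventilated, first day not found | None in 17.2.2.6; section 18 by default | Censored, if section 18 is read literally |

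Nothing in the SAP keeps the third patient as an event.

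**Inputs for the illustration**

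The SAP gives no ventilation risk and no undated share, so it has no figure to reproduce.
- From the SAP: 28 days of follow-up (8.8), 500 RDV patients (10 and 17.2.1), and up to four controls each (8.7), so at most 2000.
- Assumed: 28-day risk of 15% (range 10% to 25%), undated share u of 5% to 30% of ventilated patients, constant hazard, true hazard ratio 1, undated patients censored at day 28.

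**Events lost**

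Lost events = 500 × risk × u.
- Low end: 500 × 0.10 × 0.05 = 2.5.
- Middle: 500 × 0.15 × 0.20 = 15 of 75. Reported incidence falls to 60/500 = 12%, against a true 15%.
- High end: 500 × 0.25 × 0.30 = 37.5 of 125.

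**Precision with equal shares**

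The SE of the log hazard ratio is about √(1/d₁ + 1/d₀), where d₁ and d₀ are the event counts.
- All events kept: √(1/75 + 1/300) = 0.129.
- 20% undated in both groups: √(1/60 + 1/240) = 0.144, about 12% larger.

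The hazard ratio barely changes. In a simulation of 400,000 patients per group with risks of 10.5% and 15%, it is 0.685 with no undated events and 0.686 with 20% undated in both groups.

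**Bias with unequal shares**

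- Daily hazard: −ln(0.85)/28 = 0.005804.
- Time at risk per patient: 0.15/0.005804 = 25.84 days.
- Mean onset among the ventilated: (25.84 − 0.85 × 28)/0.15 = 13.6 days.
- Each undated patient therefore adds 28 − 13.6 = 14.4 false event-free days.
- Observed rate at share u: 0.15(1 − u)/(25.84 + 0.15 × 14.4 × u).

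| Undated, RDV / control | Rates | Ratio (true 1) |
|---|---|---|
| 10% / 20% | (0.135/26.06)/(0.120/26.27) | 1.13 |
| 20% / 10% | inverse | 0.88 |
| 10% / 30% | (0.135/26.06)/(0.105/26.49) | 1.31 |

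A smaller simulation with earlier onset (mean 4 days) and fitted Cox models gave an inflation factor of about 1.12 for 10%/20% and a hazard ratio of 1.29 for 10%/30%.

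**Against sampling error, 500 versus 2000**

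- 10%/20%: events 67.5 and 240, SE √(1/67.5 + 1/240) = 0.138. Shift ln(1.13)/0.138 = 0.9 SE.
- 10%/30%: events 67.5 and 210, SE 0.140. Shift ln(1.29)/0.140 = 1.8 SE.

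**The case against.** The strongest answer is that the SAP never says a known ventilation is to be censored. Section 17.2.2.6 limits censoring to patients not recorded as ventilated, and a specific rule normally overrides a general one. The section 18 sentence can be read as keeping partial follow-up from patients with incomplete data. This reading is open, so a reader should not infer that the SAP deliberately recodes known events. Under it, however, the undated patient has no rule at all, and the same wording is still needed.

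Second, few such patients may exist. The only field mapping in the document, the Appendix table for day-15 status, places every ventilation field on the Daily Treatment CRF, which belongs to a given day. If outcomes 7 and 8 use that form too, anyone counted there has at least one dated ventilated day, and what remains is whether it was the first. A reader might infer that outcome 6 must contradict outcomes 7 and 8. The SAP does not support that, because it names no source for them. The conflict is conditional.

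Third, no censoring time is stated, and day 28 adds the most false event-free time. This matters for that extra time but little for the hazard ratio. With censoring at the true onset, time at risk is unchanged and 10%/20% still gives 0.90/0.80 = 1.125.

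Finally, section 18 promises to document missing-data decisions. That helps, but a decision made after seeing the data does not replace a rule that can be fixed now.

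**Conclusion.** The point stands as a gap whose only stated default is unsuitable. Taken literally, section 18 drops a known event from time-to-first ventilation.

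The size cannot be fixed from the SAP. Over the assumed ranges, 2.5 to 37.5 events per 500 patients would be lost. With equal undated shares the cost is precision and an understated incidence. With a 10-point difference at 15% risk, a true hazard ratio of 1 becomes about 1.12 to 1.13 or about 0.88, depending on which group is harder to date. Section 17.2.2.5 would accept a 10-point difference in missing Daily CRFs for the oxygen outcome, though that is not the same quantity as the undated share.

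Two stronger conclusions are tempting and not supported. One is that the hazard ratio will be biased: that needs unequal undated shares, for which the SAP gives no figure. The other is that deaths or discharges without dates would be lost in the same way: nothing in the document suggests those dates will be missing. Only this secondary outcome is affected; 14-day mortality is not.

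**What to change.** In 17.2.2.6, state that any patient recorded as ventilated within 28 days of baseline, on any form, is an event. Where the first day is missing, bound it between the last Daily CRF without ventilation and the first record showing it. Assign a date by a pre-specified rule, for example the midpoint, and repeat the analysis with each end of the interval.

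A lower bound should exist for every patient in the main cohort, because 8.4.2 excludes both a missing Day 1 Daily Treatment CRF and ventilation in the first 24 hours. Using neighbouring forms also matches the SAP's own practice in 17.2.2.4 and 17.2.2.5.

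In section 18, limit the censoring sentence to patients whose event status is unknown. In 17.2.2.6 to 17.2.2.8, name the forms that define ventilation. Report the number of undated events by group.

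The cost is a few sentences and a derivation rule on forms already collected. Assigned dates carry some error, which is larger when the interval is wide; the two end-point analyses show how much that matters.

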## 19. Additional analyses

The analyses described above will be reproduced for the subgroup of patients that were ventilated during the 1st 24 hours post baseline. The sample size is expected to be small, so analyses may be simplified and/or restricted to descriptive statistics.

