### 8.2. Treatments studied

The key treatment of interest is RDV, given to patients at the early stage of a COVID-19 infection who have a high probability of developing severe disease. Guidelines were in place for its use in the UK – it was recommended for newly hospitalised patients, no later than within 10 days of symptom onset, and only initiated in non-ventilated patients. Patients were recommended to receive 200mg on Day 1 of treatment, followed by 100mg daily for 4 days. An optional additional 5 days of 100mg daily was recommended till 29th September, but the wording changed over time:

26th May to 2nd June: “If a patient does not demonstrate clinical improvement”

3rd June to 28th September: “If a patient deteriorates and progresses to ventilation and/or ECMO treatment”

29th September onwards: “Ensure that clinicians prescribe a maximum treatment course of 5 days” – this was due to a disruption in supply of the drug. It is stated that some exceptions may receive additional doses, but these were undefined by the guidelines.

The comparison treatment is: Standard of care, without RDV.

NB: Standard of care evolved as knowledge of the disease and how to treat it evolved. Co-medication with the corticosteroids dexamethasone and hydrocortisone became recommended for some patients part-way through our study period – these are not expected to interact with RDV, and so we expect that RDV patients will have received these in the same way as non-RDV patients. The drugs Hydroxychloroquine and Chloroquine phosphate were not recommended as concomitant medications for RDV from 3rd September 2020.

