##### 8.4.2. Exclusion criteria

- Requiring a high flow cannula, any ventilation or ECMO during first 24 hours post baselinec
- Pregnant
- Chronic kidney disease
- RDV initiated  $> 24$  hours post baselined
- Is a COVID-19 re-admission (was previously hospitalised for COVID-19)
- Missing Day 1 Daily Treatment CRF
- Missing ‘Medication’ section of the Outcome CRF

---

a RDV was recommended in people aged 12 and over, and weighing over 40kg. Weight was not generally measured at baseline for practical reasons, so we have excluded children aged 12-17 in order to be sure that no-one in the control group was likely to weigh less than 40kg.

b This criteria is an ideal, to measure the effectiveness of RDV initiated close to baseline. If RDV is more routinely given later than this, we will either remove this criteria, or move the window of inclusion to say 3 days. Statistics describing when RDV treatment was initiated compared with baseline, will be presented.

c This subgroup will be analysed separately (see Section 19).

d See footnote b above.

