### 9.2. Secondary Outcomes

Secondary outcomes are:

1. Time-to-recovery, where recovery is defined as: discharge from hospital or continued hospitalisation with no on-going health-care needs related to COVID-19
2. 28-day mortality
3. Time-to-death
4. Clinical status at day 15e
5. Length of time receiving supplementary oxygen
6. Time-to-first ventilation
7. Use of non-invasive ventilation at any time during 28 days post baseline
8. Use of mechanical ventilation / ECMO at any time during 28 days post baseline
9. Acute renal injury/acute renal failure at any time during 28 days post baseline
10. Liver dysfunction at any time during 28 days post baseline

Note: length of hospital stay was a key outcome of the SOLIDARITY trial, but is not listed as an outcome here. This is because our cohort includes hospital acquired COVID patients, and some patients with long-term institutionalisation. We are more interested in COVID-related hospital stay, but data on this are not collected beyond 28 days, and so we use the outcome ‘Time-to-recovery’ to double as inference to test whether RDV impacts on short-term length of stay.

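### Section 19 repeats the ventilation outcomes in patients selected for early ventilation, and its subgroup does not match the exclusion it is meant to pick up

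*SAP*

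**What the plan says.** Section 19 extends the whole analysis to one further group: "The analyses described above will be reproduced for the subgroup of patients that were ventilated during the" first 24 hours. The only latitude it gives is tied to numbers: "The sample size is expected to be small, so analyses may be simplified and/or restricted to descriptive statistics".

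The group arises from an exclusion in Section 8.4.2: "Requiring a high flow cannula, any ventilation or ECMO during first 24 hours post baseline". Footnote c to that exclusion promises: "This subgroup will be analysed separately (see Section 19".

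The analyses to be repeated include three ventilation outcomes, all counted from baseline:
- Outcome 6, time-to-first ventilation (17.2.2.6): "The DAILY CRF will be used to define, where possible, date of first use of ventilation".
- Outcome 7 (9.2 and 17.2.2.7): "Use of non-invasive ventilation at any time during 28 days post baseline".
- Outcome 8 (9.2 and 17.2.2.8): mechanical ventilation or ECMO over the same 28-day window.

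On treatment, Section 8.2 describes UK guidelines under which RDV was recommended for newly hospitalised patients "and only initiated in non-ventilated patients". Section 8.3 sets baseline at hospitalisation due to COVID (or the positive test, if hospital acquired) and notes that this need not be when RDV began.

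**The concern.** A subgroup defined by ventilation in the first 24 hours cannot also be studied for first ventilation. It can be studied for any use of a ventilation modality only if use at entry is set apart from later use. Section 19 does neither. Its outcome 7 and 8 results could be read as RDV effects on progression when they partly describe entry state.

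Two further points bear on who is compared. The Section 19 wording is narrower than the exclusion that feeds it, so a stratum promised a separate analysis may get none. And because RDV start is not baseline, an RDV patient may have joined the subgroup by deteriorating after treatment began, while a control may have been ventilated on arrival.

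This matters because Section 6.2 reports no benefit in initially ventilated patients in both trials, and Section 11 says the outcomes were chosen to allow direct comparison with those trials. Readers are likely to use this subgroup for that purpose.

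**Working it through.** Section 19 gives no figure to reproduce, so the check compares the entry condition with each outcome's definition and window.

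**Outcome 6.** Entry requires ventilation between hour 0 and hour 24, and the event is first ventilation after baseline. The event proportion by hour 24 is therefore 100% in both groups, and nobody remains at risk afterwards. A Cox hazard ratio could reflect only ordering within the first day.

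**Outcomes 7 and 8.** Let f be the share of the subgroup on non-invasive ventilation only during the first 24 hours. The SAP gives no value, so f is varied. Events already present at entry are at least f for outcome 7 and 1 − f for outcome 8.

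To show the dilution in outcome 8, assume that 20% (RDV) and 30% (control) of patients on non-invasive ventilation only go on to mechanical ventilation/ECMO, with 100 patients per group. All three values are illustrative. With entry events counted:

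- RDV: p1 = (1 − f) + 0.20f
- Control: p0 = (1 − f) + 0.30f
- OR = [p1/(1 − p1)] / [p0/(1 − p0)]
- Power (two-sided 5%, normal approximation, p̄ the mean of p1 and p0) = Φ{[|p1 − p0| − 1.96√(2p̄(1 − p̄)/100)] / √[(p1(1 − p1) + p0(1 − p0))/100]}

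| f | Outcome 7 met at entry (at least) | Outcome 8 met at entry | p1 | p0 | OR | Power |
|---|---|---|---|---|---|---|
| 1.00 | 100% | 0% | 0.200 | 0.300 | 0.58 | 37% |
| 0.75 | 75% | 25% | 0.400 | 0.475 | 0.74 | 19% |
| 0.50 | 50% | 50% | 0.600 | 0.650 | 0.81 | 11% |
| 0.25 | 25% | 75% | 0.800 | 0.825 | 0.85 | 7% |

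Entry mix can also produce an apparent effect where none exists. Suppose progression is 30% in both groups, with f = 0.75 in RDV patients and f = 0.50 in controls. Then p1 = 0.25 + 0.75 × 0.30 = 0.475 and p0 = 0.50 + 0.50 × 0.30 = 0.650, and OR = (0.475/0.525)/(0.650/0.350) = 0.49. The propensity model in Section 8.7 includes HDU/ICU admission at baseline but not type of respiratory support, so matching need not remove such a difference.

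**Who is in the subgroup.** Section 8.4.2 lists high flow cannula, any ventilation and ECMO as separate items, and footnote c sends all of them to Section 19. Section 19 names only ventilated patients. Read as written, patients on high flow alone leave the main cohort and are not picked up; the same holds for any patient on ECMO without ventilation. The Appendix also records high-flow cannula in its own CRF field.

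**Order of RDV and ventilation.** Under the guidelines in 8.2, RDV started in patients not ventilated at that moment. Those who started RDV and were then ventilated within 24 hours of baseline enter Section 19 through a post-treatment event. Others may have had RDV off guideline while ventilated, or been ventilated, come off, and then started RDV. The SAP gives no shares and does not separate these cases.

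**The case against.** The strongest reply is that this is a small supplementary analysis with flexibility built in. Section 19 allows simplified or descriptive reporting, Section 7 calls the plan an ideal case to be adapted with changes recorded, and the objectives in 7.1 and 7.2 concern non-ventilated patients only. That limits the consequence, but it does not remove the problem. The stated reason for simplifying is sample size, no ventilation outcome is dropped or redefined, and describing a 100% event proportion does not make it informative.

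Three stronger readings are tempting and are not supported:

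- *All three ventilation outcomes are degenerate.* Only outcome 6 is. Outcomes 7 and 8 are already met only by patients who entered on that modality, and progression from non-invasive to mechanical ventilation remains a meaningful question.
- *RDV patients in the subgroup were all, or mostly, ventilated after RDV start.* Section 8.2 reports a guideline, and Section 15 plans a count of patients not treated according to it. Even full adherence allows RDV after ventilation has ended, more so if the initiation window is widened as footnote b permits.
- *High-flow patients are certainly lost.* The SAP uses the term loosely: 7.1 calls the main cohort non-ventilated although 8.4.2 also removes high-flow patients, and the Appendix puts high flow and non-invasive ventilation together in score 6. A broad reading of Section 19 is possible. The conflict is one of wording, but it decides who is analysed.

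HDU/ICU admission in the propensity model gives partial control for severity on arrival. It does not identify entry modality or the order of RDV and ventilation.

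**Conclusion.** The point holds, at the level of a change that should be made before the subgroup is analysed. Outcome 6 is uninformative in ventilated patients by definition, with no assumption needed. Outcomes 7 and 8 are diluted and open to confounding by entry modality. The size depends on f and the progression rates, which the SAP does not give; the odds ratios of 0.74 to 0.85 in place of 0.58, and of 0.49 with no effect, are illustrations and not estimates for this study. Section 19 conflicts with 8.4.2 and footnote c and must be reconciled with them. Subgroup membership may be a post-treatment event for some RDV patients, in an unknown share. The primary analysis and the main-cohort secondary analyses are unaffected.

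**What to change.** Amend Section 19 as follows.

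1. Define the subgroup by the exclusion in 8.4.2 and footnote c. Report patients on high flow cannula only as a separate stratum in which outcomes 6 to 8 still apply, and state that high flow alone does not count as ventilation for those outcomes.
2. In patients ventilated or on ECMO in the first 24 hours, drop outcomes 6 and 7. Analyse outcome 8 only as new mechanical ventilation/ECMO after 24 hours, among those not on it in the first 24 hours.
3. Where dates allow, tabulate RDV patients by whether ventilation came before or after RDV start, with a row for order not determinable. Present the RDV versus control comparison in ventilated patients as descriptive.

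The cost is SAP wording, one tabulation and an entry in Change Control. A few estimates in a subgroup already expected to be small are given up; for outcome 6 in ventilated patients nothing informative is lost. The outcome 8 analysis will rest on fewer patients, which should be stated beside it.
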